**11.0 Provisions to Monitor the Data to Ensure the Safety of Subjects\***

Purpose of Data and Safety Monitoring Plan:

The purpose of the data and safety monitoring plan is to establish standards that will ensure that this protocol complies with Federal Regulations, Health Insurance Portability and Accountability Act (HIPAA) requirements and applicable Dana Farber Harvard Cancer Center (DF/HCC) Standard Operating Procedures.

**PROTOCOL TITLE: Proof-of-Concept Trial of a Positive Psychology Intervention for Caregivers of Patients with Hematologic Malignancies Undergoing Hematopoietic Stem Cell Transplantation**

**General Roles and Responsibilities:**

[name] will be responsible for all aspects of conducting the protocol, which includes:

- Overseeing the development, submission, and approval of the protocol as well as subsequent amendments.
- Ensuring that the research team members are qualified and appropriately resourced to conduct the protocol.
- Training the clinical research coordinators prior to enrolling participants and throughout the trial's conduct as needed.
- Monitoring the progress and overall conduct of the study.
- Reviewing data collection and entry, and maintaining timely submission of data for study analysis.
- Ensuring compliance with all requirements as set forth in the Code of Federal Regulations, Dana Farber Harvard Cancer Center requirements, HIPAA requirements, and the approved protocol.
- Committing to provisions that the protocol will not be rewritten or modified by anyone other than the overall PI.
- Monitoring accrual and address concerns if accrual goals are not met.

The Dana-Farber Cancer Center is expected to comply with all applicable federal regulations and requirements, the protocol and HIPAA requirements. Specifically, it will be responsible for:

- Overseeing the data collection process.
- Maintaining documentation of Serious Adverse Events (SAE) reports and deviations/violations.
- Maintaining regulatory documents which include but not limited to the following: IRB approvals/notifications, confirmation of Federal wise Assurances (FWAs), all SAE submissions, screening logs, IRB approved consents.
- Conducting regular communications with overall PI and maintain documentation of all relevant communications.
- Documenting the delegation of research specific activities to study personnel.
- Maintaining regulatory files.
- Having office space, office equipment, and internet access that meet HIPAA standards.
- Participating in quality assurance activities and meet with monitors or auditors at the conclusion of a visit to review findings.
- Providing follow-up and/or corrective action plans for any monitoring queries or audit findings.

**Intervention Training and Supervision:**

- Study Staff Training: We will conduct a full day training for the clinical research coordinator (CRC) to ensure consistent recruitment and enrollment procedures. We will train the CRC to: 1) identify potentially eligible patients via the transplant clinic schedule and/or database; 2) track potentially eligible patients; 3) communicate with the treating clinicians about patient eligibility; 4) obtain verbal informed consent from patients; 5) monitor participants longitudinally and administer study questionnaires; and 6) deliver the PATH intervention. In addition, [name] will meet with the CRC weekly to address any study issues or concerns.
- Assessment of Intervention Fidelity: To ensure the appropriate delivery of the intervention, 10% of all intervention calls will be recorded and reviewed with [name] for consistency with explanation and delivery of positive psychology exercises. These measures will also provide accurate data on

## **PROTOCOL TITLE: Proof-of-Concept Trial of a Positive Psychology Intervention for Caregivers of Patients with Hematologic Malignancies Undergoing Hematopoietic Stem Cell Transplantation**

intervention feasibility. [name] will also discuss any issues or concerns regarding the intervention fidelity.

### Informed Consent Requirements:

The Dana Farber Harvard Cancer Center approved informed verbal consent document will serve as a template for the informed consent.

Protocol Confidentiality: All documents, investigative reports, or information relating to study participants will be kept strictly confidential. We will ensure confidentiality is maintained by identifying participants on all study materials only by participant number, visit number, and date of visit. By recording study data in this manner, all information will be considered 'de-identified,' and therefore compliant with the Standards for Privacy of Individually Identifiable Health Information ("Privacy Rule") of the Health Insurance Portability Act of 1996. We will keep participant data in a computer file that is password protected. Only [name] and research team will have access to the data. We will maintain a link between the participant name and study number in a separate password protected file.

Data Management Organizational Structure: [name] and the CRC will develop the study specific database to ensure all data is entered appropriately. The CRC will routinely evaluate the data and discuss any problems and questions with [name] at a weekly meeting. Data management formal reports on record status across the three following domains will be employed: entered, verified, and edited. These reports of data records will be evaluated once a month during the final team meeting of the month. To help ensure data protection, backup copies, automatically generated by our computer systems, will be available.

Attrition Safeguards/Protection of Loss of Data: A notable methodological consideration pertaining to the proposed research is protection against attrition. Our research group has conducted numerous clinical intervention studies. In our previous work, we have learned that individuals are best retained in studies when there is 1) a familiarity with study personnel (e.g., ability to effectively establish rapport), 2) team-based persistence in conducting follow-up assessments, and 3) intervention sessions happening in tandem with ongoing medical appointments or inpatient hospitalizations. Yet, it is worth noting here a number of key issues that we have thoughtfully considered in the construction of the present proposal related to attrition. Attrition in clinical research studies overall occurs from three major sources: (a) disease worsening/mortality, (b) refusal to participate, and (c) loss of contact.

- Disease Worsening/Mortality: Not likely for this study as this is for caregivers and not patients.
- Refusal to Participate: Participants who are successfully recruited into the study but later refuse to participate in subsequent intervention sessions pose a threat to the proposed study. In our previous trial, our refusal to participate rate after study enrollment was quite low and all participants who started the intervention actually completed the all the intervention sessions. Again, the CRCs will maintain detailed records for patient refusals.
- Loss of Contact: Another source of attrition involves those subjects who are successfully recruited into the study but who cannot be located for subsequent follow-up assessments. Like attrition due to subject refusal, attrition due to loss of contact poses a threat to the proposed study. We do not anticipate this to be a major issue for the proposed study given this is a one-one feasibility study without many follow-up data collection. Also, the intensive and frequent outpatient follow-up visits for the caregivers of patients with hematologic malignancies during the first six months post-HSCT.

### **Data Safety and Monitoring Plan:**

**PROTOCOL TITLE: Proof-of-Concept Trial of a Positive Psychology Intervention for Caregivers of Patients with Hematologic Malignancies Undergoing Hematopoietic Stem Cell Transplantation**

The following procedures will be followed, in compliance with NIH requirements, to ensure the safety of study participants and the validity and integrity of data.

- **Range of Safety Reporting:** [name] will review all data pertaining to safety during the weekly research team meeting. These include adverse events (AEs) and serious adverse events (SAEs), but also other data that may reflect differences in safety such as treatment retention rates and reasons for dropout.
- **Data Repository:** [name] will oversee all aspects of data collection for the study and the CRCs will have the operational responsibility of data management. Specifically, the research team will develop a study specific data management protocol and standard operating procedures for the creation and testing of all study forms, data collection, quality control, and data extraction. These forms will be standardized. We will provide ongoing oversight of data management throughout the study, and will be responsible for generating reports and datasets for quality control and data analysis. All data management activities will utilize REDCap, a software toolset and workflow methodology for electronic collection and management of research and clinical trial data. REDCap data collection projects rely on a thorough study-specific data dictionary defined in an iterative self-documenting process by all members of the research team with planning assistance from Partners HealthCare Research Computing, Enterprise Research Infrastructure & Services (ERIS) group. REDCap provides secure, HIPAA compliant, web-based applications with an intuitive interface for users to enter data and have real time validation rules (with automated data type and range checks) at the time of entry.
- **Serious Adverse Events:** Expedited review will occur for all events meeting the FDA definition of a SAE (i.e., any fatal event, immediately life-threatening event, permanently or substantially disabling event, event requiring or prolonging inpatient hospitalization, or any congenital anomaly). This also includes any event that a study investigator judges to impose a significant hazard, contraindication, side effect, or precaution. Given that this is a supportive care study in caregivers, only SAEs that may potentially be related to the study will be reported to the IRB. All relevant information will be reported to the IRB for each SAE including information about the event and its outcome, study condition, concomitant medications, the subject's medical history and current conditions, and all relevant laboratory data. Notification by secure e-mail of all related study forms shall be made to the IRB within 24 hours of the occurrence of any SAE that might be relevant to the study. Information will be reviewed and a determination made of whether there was any possible relevance to the study interventions.
- **Non-Serious Adverse Events:** The research team will review monthly summary reports of the numbers and rates of adverse events by treatment group. These reports will include types of events, severity, and treatment phase.
- **Other Safety-Related Reports:** The research team will review weekly summary reports of treatment retention and reasons for dropout, by treatment group.

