### 9.5 Data from the Electronic Health Record

## PROTOCOL TITLE: Proof-of-Concept Trial of a Positive Psychology Intervention for Caregivers of Patients with Hematologic Malignancies Undergoing Hematopoietic Stem Cell Transplantation

Since this is a caregiver study and caregivers are not patients, we will not be obtaining any patient information from the electronic health record.

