**Weekly phone sessions for positive psychology intervention:** All participants will be asked to complete the 9 weekly PP exercises and to speak with the interventionist weekly. Weekly phone sessions will last approximately 15-20 minutes. Prior to completing each phone session, participants will be asked to rate their current level of happiness and optimism, using a 10-point Likert scale. Immediately after completing the exercise and phone session, participants will rate the ease of exercise/session completion, overall utility of the exercise/phone session, and their current levels of happiness and optimism, all using 10-point Likert scales. These calls will be recorded so that a percentage (10%) of these recordings can be reviewed by [name], to ensure that the PP intervention is being delivered as described in the protocol. Given the results of our prior PP studies in medical populations yielding a 64-85% completion rate of the exercises, our recent proof-of-concept trial (18-225) yielding 100% completion rate among HSCT recipients, and that this is a feasibility study (i.e., we want to assess participants' willingness to complete the phone sessions), we will expect participants to complete at least 6 PP exercises. In other words, if a participant completes at least 6 sessions, missed sessions will not be considered a deviation from the protocol.

**Follow-up assessments:** At Week 9, participants will repeat self-assessment questionnaires obtained at the beginning of the study either in-person, during a routine follow-up clinic visit, over the phone, or via a REDCap survey link e-mailed to them, depending on participant's preference. A week prior to intervention completion, participants will be mailed the Actigraph GT3X+ for follow-up physical activity data collection and participants will mail back the Actigraph in prepaid envelopes we will provide. Furthermore, participants will be asked to provide feedback about the program via a recorded exit interview over the phone.

**Positive Psychology Program Content:** All phone sessions will include (a) a review of the ease and utility of the week's PP exercise, (b) a discussion of the rationale of the next week's PP exercise through a guided review of the PP manual, and (c) assignment of the next week's PP exercise. During the calls, the interventionist and participant will also review the next section of the treatment manual and prepare for the upcoming week's exercise.

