## **12.0 Withdrawal of Subjects\***

We do not anticipate any circumstances under which the subjects will be withdrawn from the research without their consent. We do not anticipate any termination of participants. When verbal informed consent is being obtained from patients, we will emphasize to participants that they can withdraw from the study at any time for any discomforts. Participants who withdraw from the study will still have their data potentially analyzed depending on when in the study they withdraw, and participants will be informed of this as well. We will ensure that contact with participants is confidential by using only the phone numbers and other contact information that are specifically allowed by the participants and not leaving study-related messages for participants unless expressly allowed by participants. Upon enrollment, we ask all participants if it is acceptable to leave voice messages on their phones, as well as the appropriate times to call them. We adhere to any and all participant requests regarding contact. If a participant requests withdrawal from the study, we will ask them if they are comfortable sharing the reason for withdrawal to ensure that there are no adverse events to report to the IRB. We will ask the study participant if they are still willing to permit the study team to continue to monitor their health record, but withdraw from all other study procedures.

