Should a participant exhibit or express distress, they will be reassured by the study staff that they need not answer any questions they find upsetting. They will also be reminded that study participation is voluntary. If participants remain distressed, the study staff will notify both the study PI and primary transplant clinician. Should several participants express distress over an individual item, the research team will review the questionnaire and contact the IRB to consider removing it from the study.

If a participant reports severe distress or suicidal ideation during the study conduct, the CRC will inform the PI. The PI will determine the need to involve social work or psychiatry and take further action as deemed necessary. The research team will review sensitive items regarding suicidal ideation within 120 hours (5 business days) of receipt of completed surveys and will report any suicidal ideation to the PI promptly. We will take all measures to ensure that participants are comfortable, and we will postpone or end intervention sessions at study participants' requests. We will also ensure that the PI or other psychiatry study staff is available to intervene if needed (due to participant discomfort or to answer specific questions about the study), during intervention sessions and assessments. We have been thoughtful to use the briefest methods necessary to assess emotional states and other outcomes to reduce participant discomfort.

As with any study, there is the risk of a breach of confidentiality of the data collected. To minimize the potential loss of confidentiality, we will employ multiple safeguards and measures. Study procedures and intervention sessions will be administered by a trained interventionist. Study participants will be assigned a unique study identification number, stored separately from personal identification information. All data, including telephone recordings and transcripts, will be securely stored in locked file drawers. All project file cabinets and computer databases will be secured in locked offices. We will ensure to not provide any data to third parties. Data will be aggregated and summary reports will be generated without any personal identification information.

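### The 24-hour SAE notice to the IRB runs from occurrence, but routine contact is weekly and no event question is stated, so related events not volunteered early would usually be late and counts may be incomplete

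*Combined protocol and SAP*

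**What the plan says.** **Reporting rule.** The Serious Adverse Events item in Section 11.0 sets notification "within 24 hours of the occurrence of any SAE that might be relevant to the study". It narrows the scope: "only SAEs that may potentially be related to the study will be reported to the IRB". The judgement on relevance is described after the notification step.

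**Contact.** Section 9.7 has caregivers speak to the interventionist weekly for nine weeks, and someone who completes at least six sessions has no deviation for those missed. Section 11.0 has safety data reviewed at a weekly team meeting.

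**Content of contacts.** The program-content list in Section 9.7 opens "All phone sessions will include (a) a review of the ease and utility of the" week's exercise, then adds the rationale for the next exercise and its assignment. The session ratings cover ease, utility, happiness and optimism. Table 4 (Section 9.6) lists demographics, questionnaires and the accelerometer. The interview topics in Section 9.4 are acceptability, content and perceived benefit.

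**Event inquiry.** Section 12.0 asks withdrawing participants for their reason "to ensure that there are no adverse events to report to the IRB". Sections 13.0 and 19.2 describe what staff do once distress, suicidal ideation or acute symptoms are shown or reported.

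**After withdrawal.** Section 12.0 would ask leavers to permit the team to "continue to monitor their health record, but withdraw from all other study procedures". Section 9.5 reasons that caregivers are not patients and says "we will not be obtaining any patient information from the electronic health record".

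**Use of the counts.** Section 11.0 calls for monthly numbers and rates of adverse events, a report on SAEs and reportable events, and event reporting to ClinicalTrials.gov. Section 13.0 adds summaries of study-related non-serious events for the IRB.

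**The concern.** A time limit that starts at occurrence can be met only if the team learns of the event almost at once. These participants are caregivers reached mainly by telephone, and no stated route is faster than the weekly call unless the caregiver makes contact or happens to be seen. Staff could follow every procedure and still breach the rule.

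The second issue is ascertainment. The plan intends to tabulate event rates, but the visible text contains no routine question that would generate them. A low count could then mean few events or few mentions, and the data could not tell the two apart.

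The third is that the only follow-up described after withdrawal relies on a record that the section on electronic health records does not provide for.

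**Working it through.** The plan states no SAE rate, detection rate or on-time reporting rate, so there is no figure to reproduce. The check is a timing calculation followed by a comparison of sections.

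**Inputs from the documents**
- Limit: 24 hours = 1 day from occurrence (Section 11.0).
- Contact gap: 7 days, with nine calls over 9 × 7 = 63 days (Section 9.7).
- Lowest attendance without a deviation: 6 of 9 calls (Section 9.7).
- Sample: 25 caregivers (Section 4.0).

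**Assumptions not in the documents**
- Event times are uniform over the intervention.
- An event not volunteered early is disclosed at the next attended call and notified at once.
- A share *s* of events is volunteered within 24 hours.

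**Step 1: events not volunteered early (*s* = 0).** Each call catches in time only events from the preceding day.
- All calls attended: 9/63 = 1/7 = 14.3% on time, 85.7% late. Mean delay is 7/2 = 3.5 days and the maximum is 7.
- Six of nine attended: 6/63 = 9.5% on time, 90.5% late.

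**Step 2: some events volunteered early.** With all calls attended, late share = (1 − *s*) × 6/7.

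| *s* | Late share |
|---|---|
| 10% | 77.1% |
| 25% | 64.3% |
| 50% | 42.9% |
| 75% | 21.4% |

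More than half are late only if (1 − *s*) × 6/7 > 0.5, that is *s* < 5/12 = 41.7%. With six of nine calls the condition is (1 − *s*) × 57/63 > 0.5, that is *s* < 44.7%.

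**Step 3: completeness.** Steps 1 and 2 assume that every event is eventually disclosed, so they say nothing about undercounting. That needs a separate quantity: the share *a* of events that are ever ascertained. The observed rate is the true rate *p* times *a*, and the chance of seeing no event in 25 people is (1 − *p* × *a*)^25. As illustration only, take *p* = 10%:
- *a* = 1: observed rate 10%, (0.90)^25 = 7.2%.
- *a* = 0.5: observed rate 5%, (0.95)^25 = 27.7%.

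The documents give neither *p* nor *a*. The example shows why an empty table is hard to interpret; it does not estimate the shortfall.

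**Step 4: health record.** Section 12.0 presupposes ongoing monitoring of the participant's record. Section 9.5, the section on data from the electronic record, plans none and gives as its reason that caregivers are not patients. Nothing in the visible text names a source for the monitoring that leavers would be asked to permit.

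**The case against.** **Scope.** A reader might infer that most SAEs in the trial would breach the limit. The documents do not support that. The rule covers only SAEs that might be study-related, and Section 13.0 anticipates none, so the affected set is small and may be empty. This stands. The rule must still be workable for any event that falls under it.

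**Timing.** The 86% depends on its assumptions. Distress from a talking intervention could cluster around sessions, when staff are on the line, and Section 13.0 keeps the investigator or psychiatry staff available then. Survey reminders (Section 9.6) and clinic visits add contacts. All of this could raise *s*, possibly past 42%. This stands, so 86% can describe only events not volunteered before the next call.

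**Ascertainment.** The list in Section 9.7 concerns program content and is not exhaustive. Section 11.0 promises operating procedures and standardized forms, and the interview guide in Appendix R is not visible. It would be too strong to say that no event question exists, or that leavers are asked and completers never are. What stands is that the visible text states none outside withdrawal. The routes in Sections 13.0 and 19.2 respond to what is shown or reported; they do not ask.

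**The 120-hour review.** Section 13.0 allows review "within 120 hours (5 business days) of receipt of completed surveys", and it is tempting to set this against 24 hours as a fivefold breach. That limit is for suicidality items and runs from survey receipt: a different event on a different clock. It is not evidence on SAE lateness.

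**Health record.** Section 9.5 speaks of patient information and Section 12.0 of the participant's record, so the conflict is not word for word. The reason given in Section 9.5 still leaves Section 12.0 without a stated source.

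**Consequence.** Section 8.0 lists no safety endpoint, and nothing says that the event count will inform the efficacy trial. This stands.

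**Conclusion.** The point holds in limited form. A limit of 24 hours from occurrence cannot be relied on with weekly contact. For potentially related SAEs not volunteered earlier, about 86% would be late with all calls attended and about 90% with six of nine, given uniform timing and disclosure at the next call. The overall late share cannot be fixed from the documents; a majority would be late only if fewer than about 42% were volunteered within 24 hours (about 45% with six of nine calls).

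Event numbers and rates may be incomplete because no routine question is stated. A reader might go further and conclude that rates will be undercounted by a known amount; the documents contain nothing from which to compute that. Sections 9.5 and 12.0 need to be reconciled.

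This is a compliance and data-quality defect in a minimal-risk feasibility study. It is worth correcting because correction is cheap, and it does not touch the feasibility or acceptability results.

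**What to change.** 1. **Section 11.0:** run the 24 hours from the study team's awareness of the SAE. The contact gap then no longer causes a breach by itself.
2. **Section 9.7:** add one scripted open question on new health problems, hospital visits or study-related upset to each weekly call and to the week-9 contact, with the answer logged in REDCap. Moving the clock does not improve completeness; this question does.
3. **Sections 9.5 and 12.0:** reconcile them on follow-up after withdrawal, for example by asking permission for one follow-up call in place of record monitoring.

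The cost is one changed phrase, about a minute on each existing call, one REDCap field and a revised sentence on withdrawal. The downside is that a few more minor events will be recorded, so the reported count may look slightly higher.
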